6.3.16. Pneumonia

All suspected pneumonias will require confirmation as defined by the presence of new infiltrate(s) on chest x-ray AND at least 2 of the following signs and symptoms:

- Increased cough
- Increased sputum purulence (color) or production
- Auscultatory findings of adventitious sounds (e.g. egophony, bronchial breath sounds, rales, etc.)
- Dyspnea or tachypnea
- Fever (oral temperature > 37.5 °C)
- Elevated WBC (>10,000/mm³ or >15% immature forms)
- Hypoxemia (HbO₂ saturation ≤88% or at least 2% lower than baseline value)

All pneumonias must be captured on the AE/SAE page of the eCRF and on the pneumonia page of the eCRF.

The investigators and site staff should remain vigilant for the possible development of pneumonia in patients with COPD as the clinical features of such infections overlap with the symptoms of COPD exacerbations. Risk factors for pneumonia in patients with COPD receiving fluticasone furoate/vilanterol include current smokers, patients with a history of prior pneumonia, patients with a body mass index < 25 kg/m² and patients with an FEV₁ < 50% predicted. For all suspected cases of pneumonia, Investigators are strongly encouraged to confirm the diagnosis (this includes obtaining a chest x-ray) and to initiate appropriate therapy as promptly as possible. All diagnoses of pneumonia (radiographically confirmed or unconfirmed) must be reported as an AE or SAE (if applicable).

Note: Pulse oximetry should be measured at any time a moderate or severe exacerbation is reported or pneumonia is suspected and recorded in the source documents and on the pneumonia page of the eCRF if applicable.

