## 6. STUDY POPULATION ANALYSES

### 6.1. Overview of Planned Analyses

The study population outputs will be based on the ITT population unless otherwise stated.

Table 2 provides an overview of the planned study population outputs, with the detailed list of data displays being presented in Section 11.12.

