**Table 2 Overview of Planned Study Population Analyses**

Display Type	Data Displays Generated		
	Table	Figure	Listing
Subject Disposition			
Study Populations and Reasons for Screen Failures	Y 		Y 
Clinic Visits (Clinic Attendance/Phone Contact)	Y		
Study Treatment Status	Y	Y 	Y
End of Study Record	Y	Y 	Y
Number of Subjects Enrolled	Y 		
Inclusion and Exclusion Criteria Deviations	Y 		Y 
Important Protocol Deviations	Y		Y
Demography			
Demographic Characteristics	Y 		Y
Race and Racial Combinations	Y 		Y
Medical Conditions			
Medical Conditions (Current/Past )	Y 		
Cardiovascular Risk Factors	Y 		
Family History of Cardiovascular Risk Factors	Y 		
Smoking History at Screening	Y 		
Smoking Status	Y 		
Pneumonia Risk Factors at Screening	Y 		
Disease Characteristics			
COPD Duration	Y 		Y
COPD Exacerbation History	Y 		Y
Screening Lung Function	Y 		
Reversibility and GOLD Grade(1-4) at Screening	Y 		
CAT Score at Screening	Y 		
Shift in CAT Score Category from Screening to Baseline	Y 		
Pulse Oximetry			
Percent Oxygen in Blood	Y		
Concomitant Medications			
COPD Medications	Y 		Y
COPD Medication Combination at Screening	Y 		
COPD Medication Combination at IP Discontinuation	Y		
COPD Medication Combination at IP Discontinuation for those Subjects Providing Off-treatment Information	Y		
Pneumonia and Influenza Vaccines Taken at Any Time up to the End of Study Treatment	Y		
Non-COPD Medications	Y 		

Display Type	Data Displays Generated		
	Table	Figure	Listing
Treatment Compliance			
Treatment Compliance	Y		
Study Population Listings			
Randomized and Actual Treatments by Country and Center			Y
Treatment Blind Broken During Study			Y
Study Treatment Misallocations			Y

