**9.2.3.2. Pneumonia Risk Factors**

Baseline characteristics to identify potential pneumonia risk factors at screening, as defined in Section 11.5.2.5, will be summarised for those subjects who have an on-treatment event in the pneumonia AESI group.

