**9.2.13.2. Time to First Event in the Pneumonia AESI Group, Cardiovascular AESI Group**

Safety Statistical Analyses Time to First Pneumonia
Endpoint

 
• Time to first on-treatment event in the Pneumonia AESI group
 
• Time to first on-treatment event in the Pneumonia AESI group resulting in hospitalization, prolonged hospitalization or death.
 
• Time to first on-treatment event in the Cardiovascular AESI group
 
• Time to first on-treatment event in the Cardiovascular AESI group resulting in hospitalization, prolonged hospitalization or death.
 

Model Specification

 
• Cox's proportional hazards model
 
• Terms in the model:               
 
• Response: time to first event in the Pneumonia/Cardiovascular AESI group (definition dependent on endpoint)
 
• Categorical: treatment group, geographical region
 
 
 
• The 'exact' method will be used for handling ties. If the analysis will not run using the 'exact' method, then the 'Efron' method for handling ties will be used instead.
 
• Kaplan-Meier survivor functions will be obtained for each treatment group using PROC LIFETEST with a TIME statement.
 

Model Checking & Diagnostics

 
• Refer to Appendix 10: Model Checking and Diagnostics for Statistical Analysis.
 

Model Results Presentation

 
• Hazard ratios (and percent reduction in risk for pairwise treatment comparisons with associated 95% CIs and unadjusted p-values will be presented.
 
• The probability of having an event, 95% CI and first quartile and median time to event for each treatment group will be presented.
 
• The Kaplan-Meier curves will be presented showing the probability of having an event over time for each treatment group separately plotted on the same figure. This will be repeated displaying FF/VI and UMEC/VI treatment groups only.
 

Example SAS Code
<pre>proc phreg data=dsetin;   class trtcd region;   model timeto1*eventflag(0) = trtcd region / risklimits ties=exact;   hazardratio trtcd / diff=all; run;  proc lifetest data=destin outsurv=survest;   time timeto1*eventflag(0);   strata trtcd; run;</pre>

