**11.5.2.5. Pneumonia Risk Factors**

Pneumonia Risk Factors at Screening

 
● The following categories will be summarized to identify pneumonia risk factors: 
 
● Age (<65, ≥65)
 
● Gender
 
● BMI (will be defined twice; <21 kg/m^2, ≥21 kg/m^2; <25 kg/m^2, ≥25 kg/m^2)
 
 
 

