1.35	ITT	Summary of Smoking History at Screening by Eosinophil Subgroup	SAC
1.36	ECG	Summary of Smoking History at Screening	SAC

Study Population Tables			
No.	Popu- lation	Title	Deliverable [Priority]
1.37	ITT	Summary of Smoking Status	SAC
1.38	ITT	Summary of Smoking Status by Eosinophil Subgroup	SAC
1.39	ECG	Summary of Smoking Status	SAC
1.40	ITT	Summary of Pneumonia Risk Factors at Screening	SAC
1.41	ITT	Summary of Pneumonia Risk Factors at Screening by Eosinophil Subgroup	SAC
Disease Characteristics			
1.42	ITT	Summary of COPD Duration at Screening	SAC
1.43	ITT	Summary of COPD Duration at Screening by Eosinophil Subgroup	SAC
1.44	ITT	Summary of COPD Exacerbation History at Screening	SAC [1]
1.45	ITT	Summary of COPD Exacerbation History at Screening by Eosinophil Subgroup	SAC
1.46	ITT	Summary of COPD Exacerbation History at Screening by Country	SAC
1.47	ITT	Summary of COPD Exacerbation History Details at Screening	SAC
1.48	ITT	Summary of COPD Exacerbation History Details at Screening by Eosinophil Subgroup	SAC
1.49	ITT	Summary of COPD Exacerbation History Details at Screening by Country	SAC
1.50	ITT	Summary of Screening Lung Function	SAC [1]
1.51	ITT	Summary of Screening Lung Function by Eosinophil Subgroup	SAC
1.52	ITT	Summary of Screening Lung Function by Country	SAC
1.53	ITT	Summary of Reversibility and GOLD Grade (1-4) at Screening	SAC
1.54	ITT	Summary of Reversibility and GOLD Grade (1-4) at Screening by Eosinophil Subgroup	SAC
1.55	ITT	Summary of Reversibility and GOLD Grade (1-4) at Screening by Country	SAC
1.56	ITT	Summary of CAT Score at Screening	SAC
1.57	ITT	Summary of CAT Score at Screening by Eosinophil Subgroup	SAC
1.58	ITT	Summary of Shift in CAT Score Categories from Screening to Baseline	SAC
1.59	ITT	Summary of Shift in CAT Score Categories from Screening to Baseline by Eosinophil Subgroup	SAC
Pulse Oximetry			
1.60	ITT	Summary of Percent Oxygen in Blood at Visit 2, Pre-Dose	SAC
Concomitant Medications			
1.61	ITT	Summary of COPD Concomitant Medications Taken Prior to Screening	SAC
1.62	ITT	Summary of COPD Concomitant Medications Taken in the Run-in, Medications Given for Reasons other than an Exacerbation	SAC
1.63	ITT	Summary of On-treatment COPD Concomitant Medications, Medications Given for Reasons other than an Exacerbation	SAC
1.64	ITT	Summary of Post-treatment COPD Concomitant Medications, Medications Given for Reasons other than an Exacerbation	SAC

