3.028	ITT	Summary of Adjudicated On-treatment Serious Adverse Reports	SAC
3.029	ITT	Summary of Adjudicated On-treatment Non-fatal Serious Adverse Reports	SAC
3.030	ITT	Summary of Adjudicated On-treatment Fatal Serious Adverse Reports	SAC
3.031	ITT	Summary of Adjudicated Post-treatment Serious Adverse Reports	SAC
3.032	ITT	Summary of Adjudicated Post-treatment Non-fatal Serious Adverse Reports	SAC
3.033	ITT	Summary of Adjudicated Post-treatment Fatal Serious Adverse Reports	SAC
Adverse Events of Special Interest			
3.034	ITT	Summary of On-treatment Adverse Events of Special Interest	SAC [1]
3.035	ITT	Summary of On-treatment Adverse Events of Special Interest by Eosinophil Subgroup	SAC
3.036	ITT	Summary and Analysis of Time to First On-treatment Event in the Pneumonia AESI Group	SAC
3.037	ITT	Summary and Analysis of Time to First On-treatment Event in the Pneumonia AESI Group by Eosinophil Subgroup	SAC
3.038	ITT	Summary of Pneumonia Risk Factors at Screening for Subjects with an Event in the Pneumonia AESI Group	SAC
3.039	ITT	Summary of Pneumonia Risk Factors at Screening for Subjects with an Event in the Pneumonia AESI Group by Eosinophil Subgroup	SAC
3.040	ITT	Summary and Analysis of Time to First On-treatment Event in the Cardiovascular AESI Group	SAC
3.041	ITT	Summary of Incidence of On-treatment Pneumonia AESI and Adjudicated Pneumonia	SAC
Serious Adverse Events of Special Interest			
3.042	ITT	Summary of On-treatment Serious Adverse Events of Special Interest	SAC
3.043	ITT	Summary of On-treatment Fatal Serious Adverse Events of Special Interest	SAC
3.044	ITT	Summary and Analysis of Time to First On-treatment Event in the Pneumonia AESI Group Resulting in Hospitalization/Prolonged Hospitalization or Death	SAC

Safety Tables			
No.	Popu- lation	Title	Deliverable [Priority]
3.045	ITT	Summary and Analysis of Time to First On-treatment Event in the Cardiovascular AESI Group Resulting in Hospitalization/Prolonged Hospitalization or Death	SAC
MACE			
3.046	ITT	Summary of On-treatment Major Adverse Cardiac Events (MACE) – Narrow Definition	SAC
3.047	ITT	Summary of On-treatment Major Adverse Cardiac Events (MACE) – Broad Definition	SAC
Pneumonia (eCRF Pneumonia Form)			
3.048	ITT	Summary of On-treatment Pneumonia Incidence	SAC
3.049	ITT	Summary of On-treatment Details of Pneumonia	

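### The SAP's pneumonia risk-factor summary covers pneumonia cases only; no planned display gives pneumonia incidence or rate by risk factor and arm, and the pneumonia Cox model omits the known prognostic factors

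*SAP*

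**What the plan says.** Protocol 6.3.16 lists the traits already linked to pneumonia: "Risk factors for pneumonia in patients with COPD receiving fluticasone furoate/vilanterol include current smokers, patients with a history of prior pneumonia", plus BMI below 25 kg/m² and FEV1 below 50% predicted. Protocol 1.3.1 gives the same list and says that pneumonia will weigh in the benefit-risk assessment.

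SAP 11.5.2.5 opens with "The following categories will be summarized to identify pneumonia risk factors" and lists age, gender, BMI (split at 21 and again at 25 kg/m²), smoking status, pneumonia history and GOLD grade. Two sets of tables use these categories:

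- **Cases.** SAP 9.2.3.2 says the traits "will be summarised for those subjects who have an on-treatment event in the pneumonia AESI group". In SAP 11.12.7 this is Table 3.038, "Summary of Pneumonia Risk Factors at Screening for Subjects with an Event in the Pneumonia AESI Group", repeated by eosinophil subgroup as Table 3.039.
- **Everyone.** SAP 11.12.3 lists Table 1.40, "Summary of Pneumonia Risk Factors at Screening", for the ITT population, repeated by eosinophil subgroup as Table 1.41.

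In SAP 9.2.13.2 the categorical terms of the Cox model for time to first pneumonia event are "treatment group, geographical region", with no continuous terms. The only planned effect modifier for pneumonia is eosinophil subgroup (SAP 9.2.13.3).

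**The concern.** The share of cases with a trait mixes how common the trait is with how risky it is. A frequent, harmless trait fills a case-only table; a rare, harmful one hardly shows. A summary meant to find risk factors needs subjects at risk beside the cases and, because follow-up is on-treatment, time at risk as well. Neither appears in Tables 3.038 and 3.039, and Tables 1.40 and 1.41 supply only the subject counts.

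Pneumonia is a class concern for inhaled corticosteroids, and the protocol names the patients at higher risk. For the benefit side, SAP 7.3.1.2 tests whether the treatment effect on exacerbations varies with gender, exacerbation history, smoking, region and % predicted FEV1. For pneumonia the plan tabulates no incidence by the named traits and puts none of them in a model. The study report would then leave readers to assemble the incidence figures themselves.

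**Working it through.** The plan gives no event count, power or precision for this analysis, so there is no figure of its own to reproduce. The prevalences and risk ratios below are assumptions.

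**Inputs from the documents.** Arms of 4,000, 4,000 and 2,000 (protocol 8.2.1). Earlier pneumonia incidence of 6–7% on FF/VI and 3% on VI alone (protocol 1.3.1). If the 3% carried over to UMEC/VI, expected cases would be 4,000 × 0.06 to 0.07 = 240 to 280 per ICS arm and 2,000 × 0.03 = 60 on UMEC/VI.

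**Step 1: what a case-only table shows.** With trait prevalence f and risk ratio RR, the share of cases carrying the trait is f·RR / (f·RR + 1 − f).

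| f | RR | Share of cases |
|---|---|---|
| 10% | 2 | 0.20/1.10 = 18% |
| 15% | 2 | 0.30/1.15 = 26% |
| 35% | 1.5 | 0.525/1.175 = 45% |
| 65% | 1 | 0.65/1.00 = 65% |
| 65% | 0.8 | 0.52/0.87 = 60% |

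Read alone, the third row has 55% of cases without a real risk factor, and the last has 60% of cases with a protective trait.

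**Step 2: set cases against the ITT counts.** Take one 4,000-subject arm at 6.5%, which gives 260 cases.

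- f = 35%, RR = 1.5: 116 cases among 1,400 carriers (8.3%) and 144 among 2,600 others (5.5%).
- f = 65%, RR = 0.8: 155 among 2,600 (6.0%) and 105 among 1,400 (7.5%).

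The correct direction returns in both. Tables 3.038 and 1.40 together therefore allow crude incidence by trait, and by arm if both are shown by treatment group.

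**Step 3: what the division leaves out.** Events count as on-treatment only up to one day after treatment stop (SAP 11.3.3), so categories or arms with different discontinuation have different time at risk. SAP 11.5.4.2 puts events per 1,000 subject-years on most adverse-event displays, and SAP 11.5.1.5.2 defines the denominator. Neither is applied by risk factor. The hand calculation also brings no planned interval and no adjustment for other traits.

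**Step 4: the Cox model.** Treatment is randomised, so leaving baseline factors out does not confound the arm comparison. The model simply cannot estimate a factor's effect or its interaction with treatment, and it does not use the prognostic information already collected.

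**Step 5: how far interactions can go.** Assume f = 35%, a factor RR of 1.5 and 3% incidence on UMEC/VI, with a treatment RR of 3 in carriers and 2 in others. Expected cases are about 161 and 133 in an ICS arm and 27 and 33 on UMEC/VI. The ratio of case odds is 1.50. Its log standard error is √(1/161 + 1/133 + 1/27 + 1/33) ≈ 0.285, so the 95% limits are about ×/÷ 1.75, or 0.86 to 2.6. An interaction of that size would be estimated but not established.

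**The case against.** The strongest reply is that the denominators are planned. SAP Table 2 lists "Pneumonia Risk Factors at Screening" as a table, and SAP 6.1 states that "The study population outputs will be based on the ITT population unless otherwise stated". Table 3.038 gives numerators and Table 1.40 denominators; a reader comparing 15% of the population with 26% of cases sees the enrichment at once. Because treatment is randomised, the case split by arm even carries the treatment-by-factor interaction on the risk-ratio scale. All this stands. A reader might infer that the plan cannot show who carries the pneumonia risk, or that its tables will point the wrong way. The documents do not support either reading once the two tables are put together.

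Two further replies also stand. Protocol 8.3.5.2 asks for Cox models of time to first pneumonia event and names no covariates, so the region-only model complies. Identifying risk factors is not a trial objective. A reader might also infer that the region-only hazard ratio is biased, or that on-treatment censoring distorts it through traits that drive both stopping and pneumonia. Randomisation answers the first. For the second, no figure in either document shows such a link, and SAP 11.5.4.8 applies the same censoring rule to its other first-event safety analyses.

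The reply does not supply the missing display. Nothing in the plan joins the two tables or adds person-time, and the SAP does not state for these two tables that they are shown by arm; the treatment display order in SAP 11.4.1.1 makes that likely, not certain. The composite model in SAP 9.2.13.4 adjusts for smoking and % predicted FEV1. Exacerbation is one of its components, which may explain the choice, but it shows that both variables are ready for use.

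**Conclusion.** The point holds as a gap in presentation and modelling. The one summary offered for identifying pneumonia risk factors is restricted to cases; no listed display gives incidence or an exposure-adjusted rate by factor and arm; and none of the factors in SAP 11.5.2.5 enters the pneumonia Cox model.

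The size is moderate. Crude incidence can be rebuilt from Tables 1.40 and 3.038, assuming both are shown by arm. What is lost is the exposure adjustment, planned intervals, factor effects, and some precision in the treatment comparison. The worked percentages depend on assumed prevalences and risk ratios, and the expected case counts on the earlier 3% and 6–7% carrying over. The finding that no such display is planned rests on the SAP's table list alone.

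**What to change.** 1. **Extend Table 3.038.** For each SAP 11.5.2.5 category and each arm, show subjects with an on-treatment pneumonia AESI over N, and events per 1,000 subject-years with the SAP 11.5.1.5.2 denominator. Keep the case summary and add columns to it.
2. **Add covariates in SAP 9.2.13.2.** Put smoking status, pneumonia history, BMI, age and screening post-bronchodilator % predicted FEV1 into the pneumonia Cox model alongside region.
3. **Optional.** Add exploratory treatment-by-factor interaction terms for the four protocol-named factors (smoking, prior pneumonia, BMI, FEV1), reported with confidence intervals.

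Pairwise hazard ratios in every category should not be added. About 15 categories times 3 comparisons is about 45 estimates, and repeating them in two eosinophil strata adds about 90. With about 60 expected UMEC/VI cases, a 15% trait with doubled risk leaves 60 × 0.26 ≈ 16 cases before any eosinophil split.

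The cost is SAP wording, one larger table shell and a few model terms. No new data are needed, since the categories and the time at risk are already defined. The price is slightly more programming and wide intervals in sparse categories.

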**9.2.3.3. Pregnancy**

Any pregnancies reported during the study will be summarized in case narratives. Any pregnancy complication or elective termination of a pregnancy for medical reasons will be recorded as an AE or SAE and included in summaries and listings of AEs/SAEs.

**9.2.3.4. Oropharyngeal Examination**

Oropharyngeal examination was conducted as part of the physical examination and included in source documentation. Any adverse finding will be recorded as an AE or SAE and included in summaries and listings of AEs/SAEs.

**9.2.4. Overview of Major Adverse Cardiac Events (MACE)**

**Table 8 Overview of Planned MACE Analyses**

	Data Displays Generated		
	Table	Figure	Listing
Major Adverse Cardiac Events (MACE)			
On-treatment MACE (Narrow Definition)	Y		
On-treatment MACE (Broad Definition)	Y		

**NOTES :**

- T = Table, F = Figure, L = Listing, Y = Yes display generated.
- Stats Analysis = Represents TFL related to any formal statistical analyses (i.e. modeling) conducted.
- Summary = Represents TFL related to any summaries (i.e. descriptive statistics) of the observed raw data.
- Individual = Represents FL related to any displays of individual subject observed raw data.

**9.2.4.1. Major Adverse Cardiac Events**

Major adverse cardiac event (MACE) endpoints will be based on both eCRF and adjudicated data. The definition is shown in Section 11.5.4.9.

**9.2.5. Overview of Pneumonia Details (from the eCRF Pneumonia Form)**

**Table 9 Overview of Planned Pneumonia Details (from the eCRF pneumonia form) Analyses**

	Data Displays Generated		
	Table	Figure	Listing
Pneumonia (eCRF Pneumonia Form)			
On-treatment Pneumonia Incidence	Y 		
On-treatment Details of Pneumonia	Y 		

**NOTES :**

- T = Table, F = Figure, L = Listing, Y = Yes display generated.
  - Stats Analysis = Represents TFL related to any formal statistical analyses (i.e. modeling) conducted.
  - Summary = Represents TFL related to any summaries (i.e. descriptive statistics) of the observed raw data.
  - Individual = Represents FL related to any displays of individual subject observed raw data.
1. Repeat tables for events resulting in hospitalization, prolonged hospitalization or death

**9.2.6. Overview of the Composite Endpoints**

**Table 10 Overview of Planned Composite Endpoint Analyses**

	Data Displays Generated		
	Table	Figure	Listing
Composite endpoints			
Analysis of Time to First event in the Pneumonia AESI group or moderate/severe exacerbation Composite	Y	Y 	
Analysis of time to first severe exacerbation or event in the pneumonia AESI group resulting in hospitalization, prolonged hospitalization or death	Y	Y 	
Analysis of time to first severe exacerbation or event in the CV AESI group resulting in hospitalization, prolonged hospitalization or death or event in the pneumonia AESI group resulting in hospitalization, prolonged hospitalization or death	Y	Y 	
Percentage of subjects with an event in the pneumonia AESI group and percentage of subjects with a moderate/severe exacerbation.		Y 	

**NOTES :**

- T = Table, F = Figure, L = Listing, Y = Yes display generated.
  - Stats Analysis = Represents TFL related to any formal statistical analyses (i.e. modeling) conducted.
  - Summary = Represents TFL related to any summaries (i.e. descriptive statistics) of the observed raw data.
  - Individual = Represents FL related to any displays of individual subject observed raw data.
1. Kaplan-Meier plot displaying FF/UMEC/VI, FF/VI and UMEC/VI and repeated displaying FF/VI and UMEC/VI only

## 9.2.7. Overview of Bone Fractures

**Table 11 Overview of Bone Fracture Analyses**

	Data Displays Generated		
	Table	Figure	Listing
Bone Fractures			
On-treatment Bone Fractures	Y		

**NOTES :**

- T = Table, F = Figure, L = Listing, Y = Yes display generated.
- Stats Analysis = Represents TFL related to any formal statistical analyses (i.e. modeling) conducted.
- Summary = Represents TFL related to any summaries (i.e. descriptive statistics) of the observed raw data.
- Individual = Represents FL related to any displays of individual subject observed raw data

